#### Sample size justification

The target sample size for the proposed study is  $n=60$  ( $n=30$  per group). Power calculations were performed assuming 80% power and  $\alpha=0.05$ . With  $n=60$ , our sample can detect a minimum 28% decrease in block success in the neuromuscular block group compared to the obturator block group, assuming a 97% success rate in the obturator block group. This sample size will also be able to detect a minimum group mean difference of 7.4 on the TUG ( $SD=10.0$ ).

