#### 4. Background:

Much of the available data on obturator blocks is taken from the orthopedic anesthesia literature on patients undergoing knee surgery. To date, there are no complications (including falls) related to obturator blocks reported in the literature. ONB is performed in patients undergoing TURBT to minimize or ablate the obturator reflex [2-4].

Ultrasound guided regional anesthetic techniques have a long record of safety and efficacy, and are commonly performed for patients undergoing surgery in both the outpatient and inpatient setting.

Neuromuscular blocking medications are commonly used to prevent patient movement under general anesthesia. Use of neuromuscular agents may result in postoperative weakness, which may lead to hypoxemia and airway obstruction, complaints of muscle weakness or fatigue, longer postanesthesia care unit stays, delays in tracheal extubation, increased risk of pulmonary aspiration, and atelectasis [11]. Additionally, adductor spasm has been reported despite the use of these medications [12, 13].

Furthermore, there is a study that suggests that use of an obturator nerve block in patients undergoing TURBT may prolong time to cancer recurrence in patients with superficial bladder tumors [14]. The obturator block results in a decreased incidence of adductor spasm, which allows for optimal surgical conditions and improved tumor resection [14]. The incidence of adductor spasm during TURBTs is currently unknown. While one study has estimated the incidence to be 16.5% [18], three others have reported it to be 40-55% [13, 19, 20] in patients with posterolateral bladder tumors.

Given the presence of the adverse events associated with use of neuromuscular blocking agents and the current lack of adverse events reported with the obturator block, we are interested in conducting an investigation comparing the two approaches in a prospective and randomized manner.

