#### 5. Specific Aims:

The primary objective will be to compare the incidence of adductor spasm (also known as the obturator reflex) during transurethral resection of posterolateral bladder tumors under general anesthesia.

Secondary objectives will include assessments of leg weakness and fall risks, as measured using a handheld dynamometer and the timed up and go (TUG) test, respectively. Adverse events related to the anesthetic and surgical techniques will also be recorded.

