#### 6. Research Plan:

Veterans diagnosed with posterolateral bladder tumors will be invited to participate in the study. After obtaining written informed consent, the veteran will be randomized to receive an ultrasound-guided obturator block or a neuromuscular blocking agent after the induction of general anesthesia in an attempt to block the obturator reflex during surgery. Both techniques are commonly performed and accepted techniques for the prevention of the obturator reflex.

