#### Planned statistical analyses

All analyses will be conducted in JMP Pro 12.0 (SAS Institute, Cary, NC). Categorical measures (e.g. block success) will be summarized as percentages (%). For continuous measures (e.g. TUG, dynamometer), normally distributed measures will be summarized as means and standard deviations, and non-normally distributed measures will be summarized as median with interquartile range. Differences in block success between groups will be examined with  $\chi^2$  tests. Differences in dynamometer measurements and TUG tests will be examined through t-tests, with transformation of outcomes as necessary to satisfy assumptions of the statistical test.  $P < 0.05$  will be considered statistically significant.

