#### 8. Possible Benefits:

Because adductor spasm may interfere with tumor resection, performance of an obturator block or use of neuromuscular relaxing agents may block or ameliorate the reflex and allow for safer operating conditions and improved cancer removal. The efficacy and safety of one approach versus the other is not known. The results of this study may be used to guide clinical decisions for future patients undergoing TURBT or to conduct larger prospective studies.

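### Are 30 patients per arm too few because the 28-point detectable difference is not tied to the spasm rates cited in the Background?

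*Combined protocol and SAP*

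**What the plan says.** Section 5 (Specific Aims) makes the incidence of adductor spasm during resection under general anesthesia the primary objective. Under Planned statistical analyses in Section 6, "Differences in block success between groups will be examined with" χ² tests at P < 0.05; categorical measures are summarised as percentages. The term block success is not defined. Given the primary objective, the natural reading is that no spasm occurred.

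Under Sample size justification, with 30 per group, 80% power, α = 0.05 and 97% success in the obturator group, "our sample can detect a minimum 28% decrease in block success in the neuromuscular block group compared to the obturator block group". No source is given for the 97% or for the 28%.

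Section 4 (Background) says: "The incidence of adductor spasm during TURBTs is currently unknown". It then cites 16.5% from one study and 40–55% from three others, mentioning posterolateral tumors at the end of that sentence. It does not say what prophylaxis those patients received. It also notes that spasm has occurred despite neuromuscular blocking drugs. Section 6 says of the two methods: "Both techniques are commonly performed and accepted techniques for the prevention of the obturator reflex".

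**The concern.** A detectable difference shows only what a given sample can find. It does not show that a difference of that size is expected or is the smallest that matters. Here a 28-point fall from 97% success means 31% spasm under rocuronium, and nothing in the plan says why 31% is a reasonable figure.

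If the cited incidences are rates without prophylaxis, they would be ceilings for the rocuronium arm. At 16.5%, the trial could not see 31% even if rocuronium prevented nothing. At 40–55%, it would see 31% only if rocuronium prevented no more than 22–44% of spasms (1 − 0.31/0.40 = 0.225; 1 − 0.31/0.55 = 0.436), although the plan calls both methods accepted for prevention.

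At stake is a real advantage of the obturator block being missed and the non-significant result then being taken as equal efficacy. Section 8 says: "The results of this study may be used to guide clinical decisions for future patients undergoing TURBT".

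**Working it through.** **Inputs.** From Sample size justification: n = 30 per arm, α = 0.05, 80% power, 97% obturator success (3% spasm) and a 28% decrease. From Section 4: 16.5%, 40% and 55%. Assumptions: success means no spasm; the test is two-sided and uncorrected; 28% is absolute.

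**Formula.** With p₁ and p₂ the spasm rates, d = |p₁ − p₂| and p̄ their mean:

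power = Φ{[d − 1.96·√(2p̄(1−p̄)/n)] / √([p₁(1−p₁) + p₂(1−p₂)]/n)}

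**The plan's own figure (3% vs 31%).** p̄ = 0.17.
- Null standard error: √(0.2822/30) = 0.0970; times 1.96 = 0.1901.
- Alternative standard error: √(0.2430/30) = 0.0900.
- Power = Φ[(0.28 − 0.1901)/0.0900] = Φ(1.00) = 84%.
- Size for 80% power: (1.96·√0.2822 + 0.842·√0.2430)² / 0.28² = 2.120/0.0784 = 27.04, so 28 per arm against 30 planned.

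If 28% is relative, success is 0.97 × 0.72 = 69.8%, spasm is 30.2% and power is 82%. The smallest gap detectable with 80% power is 26.0 points by this formula and 28.8 points with Fisher's test. The stated 28% lies between them, so the plan's figure reproduces.

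**The cited rates, if they applied to the rocuronium arm.** At 16.5%: p̄ = 0.0975, and power = Φ[(0.135 − 0.1501)/0.0746] = Φ(−0.20) = 42%. The other rows use the same formula; the last column enumerates all outcomes of the uncorrected Pearson test.

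| Rocuronium-arm spasm (obturator 3%) | Approximation | Exact enumeration |
|---|---|---|
| 16.5% | 42.0% | 46.0% |
| 20% | 54.3% | 60.8% |
| 25% | 69.9% | 77.4% |
| 31% | 84.1% | 89.9% |
| 40% | 95.7% | 97.8% |
| 55% | 99.9% | 99.9% |

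Power reaches 80% at 29% spasm by the approximation and at 26% by enumeration. Against a 40% or 55% incidence without prophylaxis, rocuronium could then prevent up to 28% or 47% of spasms (1 − 0.29/0.40; 1 − 0.29/0.55), or 35% or 53% by enumeration (1 − 0.26/0.40; 1 − 0.26/0.55), with power still at 80%.

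**How conditional the low figure is.** At 16.5% in the rocuronium arm, power is 65% (approximation) or 75% (exact) if the obturator arm has no spasm at all, 52% with a likelihood-ratio χ² at 3% obturator spasm, and 20% with Fisher's test. The 42–46% is specific to 3% obturator spasm and an uncorrected Pearson test.

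**What a larger trial would cost.** For 3% vs 16.5% with 80% power the formula gives 75 per arm, so 150 in total and 90 more than planned.

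**The case for a change.** The best case for acting does not depend on the 16.5% study. Suppose the 40–55% range is right for this population but describes patients without prophylaxis. If rocuronium halved a 40% incidence, its arm would have 20% spasm and power would be 54–61%. A result such as 1/30 against 5/30 would give p = 0.085 and a 95% interval for the difference of about −3 to +30 points, which includes both no difference and the 28-point gap. On this view the rate should be justified, the interval reported, and a null result not read as equality.

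The sensitivity is real and the plan does not discuss it. The step to a required change does not hold:

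- The ceiling is an assumption. Section 4 does not say what prophylaxis the cited patients had. It reports spasm despite neuromuscular blockade, and calling a method accepted gives no efficacy rate.
- Published rates may not carry over to this trial's count. The section on the neuromuscular block group adds continuous electromyography to clinical observation, which may record events that observation alone would miss.
- An interval is good practice, but it leaves the χ² result unchanged. With 30 per arm and percentages reported, a reader can recover the counts and compute it.
- No section says that P ≥ 0.05 will be read as equal efficacy. Section 8 also allows that the results may lead to larger studies.

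**Conclusion.** The concern does not call for a change. The sample size section makes a minimum-detectable-difference claim for a fixed n, and the claim is true: power is 84–90% for 3% against 31% spasm, with 80% reached at about 26–29%. The plan promises power for no other rate, so no stated figure is missed.

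What is absent is the reasoning behind the rocuronium-arm rate and its link to the Background. That is missing explanation, in a protocol that openly says the incidence is not known. Across the cited rates, power runs from 42–46% at 16.5% to about 96% or more at 40–55%. Sizing for 16.5% would add about 90 patients on the strength of the lowest of four cited studies, without evidence that it describes either arm of this trial.

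These figures assume that block success means no spasm, that obturator spasm is 3%, that the χ² test is two-sided and uncorrected, and that the cited rates apply unchanged to the rocuronium arm. The last is the least certain, and the documents cannot settle it.

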#### Obturator block group

Standard of care: After the induction of general anesthesia, the block will be performed on the side of the posterolateral bladder tumor(s). If a patient has bilateral posterolateral bladder tumors, bilateral blocks will be performed. A time out procedure will be performed confirming the patient's identity, the proposed surgical procedure, and laterality of the tumor(s) and block procedure(s). The patient's inguinal region will be cleansed with Chlorohexidine prep solution. A 21ga Pajunk SonoPlex needle will be advanced under ultrasound guidance and 20-30mL of 2% mepivacaine will be injected using an interfascial approach. All nerve blocks will be performed by [name], who has expertise in ultrasound-guided regional anesthesia. Block time will be counted as the time from needle insertion until the completion of the injections. Any inadequate/failed blocks will be recorded. Unless clinically indicated, neuromuscular blocking agents will be avoided (with the exception of succinylcholine for tracheal intubation).

#### Neuromuscular block group

Standard of care: After the induction of general anesthesia, rocuronium (a neuromuscular blocking agent) will be administered intravenously in 5-10mg increments

titrated to a goal of 2/4 twitches. An obturator block will not be performed unless adductor spasm persists despite the administration of additional rocuronium.

Research related procedure: The incidence of block- and procedure-related adverse events, including the obturator reflex, will be recorded. In addition to clinical observation, a Nerve Integrity Monitor (Medtronic) will be used to detect adductor spasm using continuous electromyography. Adhesive skin (non-needle) electrodes will be placed on the thigh to objectively detect and record instances of adductor spasm.

Standard of care: Unless contraindicated, all patients will be extubated and transported to the post anesthesia care unit (PACU). The patients will then be discharged home or to a hospital room (per the surgical service).

Research related procedure: One hour after arrival to PACU or when discharge criteria are met (whichever comes first), repeat dynamometer measurements and TUG tests will be performed. Patients will be called 24-48 hours post procedure to inquire about falls or evidence of nerve injury, as well as patient satisfaction.

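### Six of the seven neuromuscular-blocker harms that the protocol names have no scheduled collection, so the safety comparison is incomplete and unevenly ascertained across types of harm

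*Combined protocol and SAP*

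**What the plan says.** All references are to the combined protocol and SAP.

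- **Rationale (4. Background).** "Use of neuromuscular agents may result in postoperative weakness, which may lead to hypoxemia and airway obstruction, complaints of muscle weakness or fatigue". The list continues with "longer postanesthesia care unit stays, delays in tracheal extubation, increased risk of pulmonary aspiration, and atelectasis". The section closes by motivating the comparison with the "presence of the adverse events associated with use of neuromuscular blocking agents and the current lack of adverse events reported with the obturator block".
- **Open question (8. Possible Benefits).** "The efficacy and safety of one approach versus the other is not known".
- **Objectives (5. Specific Aims).** The primary objective is the incidence of adductor spasm. The secondary objectives are leg weakness (dynamometer) and fall risk (TUG). Adverse events of the anesthetic and surgical techniques are also to be recorded.
- **Collection (6. Research Plan, Methods and the text under Neuromuscular block group).** Dynamometry and TUG are done before surgery and at about one hour after it. For adverse events: "The incidence of block- and procedure-related adverse events, including the obturator reflex, will be recorded". For follow-up: "Patients will be called 24-48 hours post procedure to inquire about falls or evidence of nerve injury, as well as patient satisfaction".
- **Analysis (Planned statistical analyses).** Tests are named for block success, dynamometry and TUG. None is named for adverse events.

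**The concern.** The harms used to motivate the trial and the harms it sets out to collect do not match. Most of the blocker harms in the Background occur at emergence or in the PACU, yet no item is scheduled there except leg strength and TUG. Two of them, slower extubation and longer PACU stay, are durations. A patient whose extubation takes longer has not obviously had an adverse event, so a general instruction to record adverse events is unlikely to yield these values.

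Nerve injury, by contrast, is asked about directly. Harms that are asked about tend to be found more fully than harms left to unprompted reporting, so the resulting safety profile would be fuller for some types of harm than for others.

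The interpretation of a planned secondary outcome is also at stake. Weakness about one hour after surgery in a patient given rocuronium may be residual blockade. Twitches are followed to titrate rocuronium, but the plan does not say that recovery before extubation, or use of a reversal agent, is recorded.

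**Working it through.** **Step 1. Set the named harms against the scheduled collection.**

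| Harm named in 4. Background | Scheduled or solicited item |
|---|---|
| Weakness or fatigue | Partly: dynamometry and TUG at about one hour; falls question at 24-48 hours. Fatigue is not asked about. |
| Hypoxemia | None |
| Airway obstruction | None |
| Longer PACU stay (a duration) | None |
| Delayed extubation (a duration) | None |
| Aspiration | None |
| Atelectasis | None |

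One of seven is partly covered and six have no scheduled item. Two of those six are durations. The remaining four are events that could reach the general adverse event record, but that record has no list, definition or time window.

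**Step 2. What 30 per arm can say about a duration.** Inputs from Sample size justification: 30 per group, 80% power, alpha 0.05 (taken as two-sided, which the plan does not state), TUG difference 7.4 with SD 10.0.

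- The plan's own figure, normal approximation: n per arm = 2 × (1.960 + 0.842)² / (7.4/10.0)² = 2 × 7.85 / 0.5476 = 28.7, so 29.
- Two-sample t-test with 30 per arm: power is 80.5% at 7.4, and the smallest difference with 80% power is 7.36. The plan's figure reproduces.
- In SD units this is about 0.74. The same figure applies to time to extubation or PACU stay if nearly all 60 patients contribute a value and the values, transformed if necessary, suit a t-test. The documents give no SD for either duration, so it cannot be turned into minutes.

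**Step 3. What 30 per arm can say about a rare event.** The documents give no event rates, so those below are assumptions.

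- No events in 30 patients: exact two-sided 95% upper limit = 1 − 0.025^(1/30) = 11.6%.
- Rate needed in the other arm for 80% power, two-sided alpha 0.05:

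| Assumed rate in one arm | Chi-square | Fisher's exact test |
|---|---|---|
| 1% | about 25% | about 28% |
| 5% | about 33% | about 35% |

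These limits come from the sample size and would be the same with a checklist. A checklist makes the counts complete and comparable; it does not make rare events testable. The durations are where scheduled collection adds most, because nearly every patient supplies a value.

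**The case against.** The strongest case on the other side has five parts.

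- **Not only block harms are asked about.** A reader might infer that follow-up is confined to the nerve block's harms. It is not. The Background itself makes weakness the starting point of the blocker's harms, and dynamometry, TUG and falls can all reflect residual weakness after rocuronium. Satisfaction belongs to neither technique. This part stands.
- **No bias is shown.** A reader might infer that the comparison is loaded against the obturator block. The follow-up text sits under the neuromuscular heading, but it refers to all patients, so both arms appear to receive the same tests and questions and each item is ascertained alike. What is uneven is the coverage of types of harm. That could disfavor the block, but no rates are given and no direction can be established.
- **The rationale is wider than safety.** A reader might infer that the trial cannot test its own rationale. The primary objective is spasm, and the Background also cites spasm despite blockers, surgical conditions and recurrence. Only the safety part of the rationale is weakly tested.
- **Adverse events of the anesthetic technique are already to be recorded.** A marked airway event would probably be noted. This stands for events but not for durations, and it leaves the events undefined.
- **Residual blockade is part of the neuromuscular arm's effect.** One-hour weakness is therefore a fair comparison between arms as it stands. Agreed; twitch count and reversal use would explain a difference and are not needed to make the comparison valid.

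**Conclusion.** The point holds as one of completeness. Of the seven blocker harms that help justify the trial, weakness is partly measured in both arms and six have no scheduled collection. General adverse event recording may pick up four of those six and would not be expected to capture the two durations. Nerve injury is the only clearly technique-specific harm that is solicited. The safety comparison is therefore incomplete and unevenly ascertained across types of harm, and no analysis of adverse events is specified.

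The primary spasm comparison and the planned tests of dynamometry and TUG are unaffected. The documents do not support a finding of bias against the obturator block. Nor does the 11.6% limit for zero events in 30 argue for a checklist, since it holds with or without one.

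The conclusion assumes that the follow-up applies to both arms, that alpha is two-sided, and that the proposed items can be read from routine perioperative records, which the documents do not state.

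**What to change.** In 6. Research Plan, in the research-related text under Neuromuscular block group, predefine one safety data set, state that it applies to both arms, and collect it identically from the perioperative record:

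- time from end of surgery to extubation;
- PACU length of stay, or time until discharge criteria are met;
- hypoxemia or airway intervention, each with a written definition;
- suspected aspiration;
- where a neuromuscular blocker was given, in either arm, the last recorded twitch count and any reversal agent given.

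In the existing 24-48 hour call, add questions on weakness or fatigue and on breathing problems, asked of all patients. Atelectasis can remain under general adverse event recording.

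In Planned statistical analyses, compare the two durations between arms by the t-test approach already planned for TUG, transforming where necessary. Report the event items descriptively by arm with exact 95% confidence intervals, and state that 30 per arm cannot compare rare events.

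The cost is a few more case report form fields and two call questions. No visit is added, and treatment and sample size do not change. The trigger for the PACU tests already depends partly on when discharge criteria are met, and twitches are already followed to titrate rocuronium, so part of the information is generated under the current plan.

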#### 7. Possible Discomforts and Risks:

In addition to the risks of general anesthesia, veterans in the obturator block group may experience the following: nerve damage, intravascular injection of local anesthetic, cardiac arrest, seizure, bleeding/hematoma, infection, ineffective or failed block, pain at the injection site, or numbness or tingling (paresthesia). These events are rare and, to date, none of these complications have been reported in patients receiving an obturator block.

Because the obturator block will be performed after the induction of general anesthesia, the enrolees should not experience any discomfort during the block procedure.

